Hepatic Steatosis Snap Shot

Sites Participating: All sites

Principal Investigator: [name] (University of Michigan)

Co-Investigators: [name]; [name]; [name];
[name]

Study Name: HEPATIC STEATOSIS IN CHRONIC HEPATITIS C: RISK FACTORS AND ROLE ON THE DEVELOPMENT OF HEPATIC FIBROSIS

Separate Consent Form: No

Withdrawal Form: No

Eligible Patients: Lead-in, Randomized, W20 Responders, Sustained Virologic responders and Breakthrough/Relapser
(Express patients are not eligible)

Visit Schedule (additional data/specimen and forms for AS)

Note: "X" means all participating sites take part.

Lead-In Phase

Visit Number →	Form #	S00	W00	W02	W04	W08	W12	W16	W20	W24
Fasting Insulin seq.121	Excel file		X							
Glycosylated Hemoglobin	121	X								

Randomized Phase

Visit Number →	Form #	R00	M12	M18	M24	M30	M36	M42	M48	M54
Fasting Insulin seq. 121	Excel file				X					
Glycosylated Hemoglobin	121									

Hepatic Steatosis in Chronic Hepatitis C: Risk factors and role in the development of hepatic fibrosis

Principal Investigator: [name]

Co-Investigators: [name], [name], [name], [name]

SPECIFIC AIMS:

The central hypothesis of this ancillary study is that hepatic steatosis plays a key role in the development of fibrosis and cirrhosis in patients with chronic hepatitis C. In addition, we hypothesize that both viral and non-viral factors are involved in the development of hepatic steatosis in patients with chronic hepatitis C, and the benefits of long-term interferon therapy is in part mediated via reduction of hepatic steatosis. The specific aims of this study are:

1. To determine the prevalence of hepatic steatosis in patients with chronic hepatitis C.
2. To determine if there is a correlation between hepatic steatosis and hepatic fibrosis in patients with chronic hepatitis C.
3. To identify viral and non-viral risk factors for hepatic steatosis in patients with chronic hepatitis C.
4. To identify metabolic predictors of week 20 and sustained virologic response
5. To determine the effects of long-term interferon therapy on hepatic steatosis in patients with chronic hepatitis C.
6. To determine the effects of virologic clearance on insulin resistance in patients with chronic hepatitis C.

RELATIONSHIP OF PROPOSED STUDY TO NIH HALT-C TRIAL

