In summary, current data indicate that hepatic steatosis is common in patients with chronic hepatitis C but the exact prevalence and severity remains to be determined. Recent studies suggest that both viral and non-viral factors may be involved in the development of hepatic steatosis in patients with chronic hepatitis C but the relative importance of these factors is not known. It has been postulated that necroinflammation and fibrosis in NASH occurs as a result of two hits [22]. The first hit is related to hyperinsulinemia due to insulin resistance causing increased free fatty acids leading to accumulation of lipids in hepatocytes. The second hit occurs when there is oxidative stress which can be induced by endotoxins, alcohol, iron and possibly HCV. In patients with chronic hepatitis C, obesity, alcohol consumption and diabetes may provide the first hit, and alcohol, iron and HCV may provide the second hit.

Emerging evidence suggests that metabolic factors play an important role not only in hepatitis C disease progression, but also in response to antiviral therapy. Increased BMI and hepatic steatosis have been associated with diminished responses to interferon and ribavirin therapy (Bressler et al, *Hepatology* 2003; 38:639; Kaserer K et al, *Histopathology* 1998;32:454). Further, weight loss has been associated with improved steatosis and fibrosis in persons with chronic HCV (Hickman IJ, *Gut* 2002;51:89). The relationship of these metabolic factors and insulin resistance with response to PEG-IFN and ribavirin therapy has not been explored. We hypothesize that hepatic steatosis and increased insulin resistance independently predict nonresponse to PEG-IFN and ribavirin therapy for chronic HCV. While other baseline factors, including BMI and weight were included in the original analysis of the HALT-C lead in patients by Shiffman et al (*Gastro* 2004; in press), we plan to focus on metabolic factors. The HALT-C cohort offers the advantage of a histologically uniform group that minimizes the confounding effect of fibrosis in this analysis.

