- c) Quantitative alcohol consumption during the study will be assessed every 6 months, Form #42, Alcohol Use Questionnaire.
- d) ♦ New diagnosis of diabetes, and/or hyperlipidemia during the study, Form #30, Local Lab, and Form #10, Study Visit.
- e) ♦ Concomitant medications that may induce hepatic steatosis, Form #12, Medications Interview.

Serial laboratory tests will be performed per protocol:

- a) Liver panel at each visit, Form #30, Local Lab.
- b) HCV RNA every 3 months, Form #31, Central Lab – HCV RNA.
- c) Fasting blood glucose every 6 months, Form #30, Local Lab.
- d) Fasting triglyceride level every 6 moths, Form #30, Local Lab.
- e) ♦ Fasting insulin level at the end of year 2 (M24) Excel file, with Fasting Insulin results.

Liver biopsies obtained at the end of year 2 (M24) and year 4 (M48) will be assessed for hepatic inflammation, fibrosis, iron and steatosis.

To address aim 6, all non-diabetic patients with TW 20 response followed until TW 60 will be included. A group of matched (BMI, race, HCV genotype) non-diabetic controls with no virologic response at TW20 will also be studied if a difference in IR is detected at TW 60 between patients with SVR and relapsers.

1. Serial clinical data at baseline, TW20, TW 48, and TW 60 for patients with TW20 virologic response, and data at baseline and TW20 for matched controls.
2. Serial laboratory tests: liver panel, HCV RNA, glucose, triglycerides as per protocol. Fasting insulin levels at TW00 and TW 60 for patients with TW20 response.

If results show a difference in IR at TW60 between patients with SVR and relapsers, fasting insulin levels at TW20 will also be tested in study subjects and matched controls.

Specimen Collection, Handling, and Shipping:

- **Blood collection and processing for insulin assays at baseline and at year 2 (M24)**

1. Collect blood in a red top tube – 7mls (Do NOT use tubes that have EDTA coating).
2. Allow the blood to clot for at least 30 minutes – this does not necessarily have to be on ice if not available (blood can be allowed to clot for up to 2-2.5 hours).
3. Spin the tube for 10-15 minutes at 3000 RPMs.

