 - Alcohol consumption: life time alcohol consumption and consumption within the year prior to the liver biopsy.
 - Viral factors: HCV genotype, HCV RNA level.
 - Hepatic inflammation: ALT level and hepatic inflammation grade.
 - Iron: serum iron, TIBC and hepatic iron score.

Risk factor data such as BMI, life time alcohol consumption, diabetes status etc. will be coded as categorical or continuous variables as appropriate. These will be evaluated against the degree of steatosis (5 levels) and dichotomous collapsed steatosis codes (such as <33% vs \geq 33%) using the Cochran-Mantel-Haenszel chi-square test with one degree of freedom. Multivariate analysis will be performed using logistic regression analysis. These risk factor variables and the steatosis levels will similarly be evaluated against the fibrosis scores (6 levels). Because fibrosis will also be quantified morphometrically, it will also be analyzed as a dependent variable by analysis of variance.

4. These risk factors and their relationship to week 20 and sustained virologic response will also be assessed.

Univariate analysis will be carried out using categorical or continuous variables as appropriate. These will be categorized against dichotomous (W20 responder v nonresponder, SVR v no SVR (all W20 nonresponders will be categorized as no SVR)) variables using the Cochran-Mantel-Haenszel chi-square test with one degree of freedom. Multivariate analysis will be performed on significant variables identified in univariate analysis by logistic regression.

Longitudinal study

The following analyses will be performed:

1. Prevalence of hepatic steatosis in year 4 biopsies will be compared to the year 2 and baseline biopsies of all patients and separately for the treated patients and controls.
2. Changes in hepatic steatosis between year 4 and baseline biopsies will be compared for the entire cohort of patients, and separately for the treated patients and controls.
3. Correlation between changes in hepatic steatosis with changes in hepatic fibrosis.
4. Correlation between changes in hepatic steatosis and changes in other risk factors for hepatic steatosis such as BMI, alcohol consumption, triglyceride level, hepatic inflammation, and hepatic iron content.
5. Correlation between changes in insulin resistance (measured using the homeostasis model assessment (HOMA)) from baseline to week 60 of the lead-in patients and virologic response or relapse.

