We will compare HOMA-IR (calculated from fasting insulin and glucose levels) from subjects at entry into the lead in phase of HALT-C and compare week 60 samples from among responders (HCV RNA undetectable) and relapsers (HCV RNA +). Because of inherent insulin resistance among diabetic patients, we will confine the analysis to nondiabetic subjects (about 80%) of those with W60 samples. This would comprise about 250 subjects with available W60 sera. These would be evenly divided between responders and relapsers (125 in each group). Changes in HOMA-IR would be calculated between the responder and relapser groups. An advantage of studying W60 sera is that any confounding effects of PEGIFN and RBV on IR will be minimized, including weight loss on therapy. If differences can be discerned between the 2 groups, then it will also be of interest to perform W20 determinations among responders and nonresponders in a larger number of subjects. A secondary analysis would include assessment of the correlation between HOMA-IR and HCV RNA levels at baseline for all subjects and at W60 for relapsers, as well as correlation of virologic response or relapse with fasting glucose levels and HgbA1c in those persons with diabetes or impaired glucose tolerance (about 20% of the group).

PITFALLS AND LIMITATIONS

This study does not involve any additional invasive tests or time commitment from the trial participants. Most of the data required will be collected as part of the main trial, so we do not anticipate there will be any problem in conducting this study. It is possible that steatosis may have no role in the development of fibrosis/cirrhosis in patients with chronic hepatitis C. However, results from studies in patients with NASH and the recent report of Hourigan support that steatosis may be important in hepatic fibrogenesis. Patients in this study will all have significant fibrosis (Ishak score ≥ 3) and non-response to prior interferon therapy. Results of our study may not necessarily apply to other patients with chronic hepatitis C. However, the patients we will be studying are at greatest risks of developing fibrosis and cirrhosis, and any factor that can promote fibrosis should be easily demonstrated in this study.

REFERENCES

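### The Aim 6 extension is triggered by insulin resistance at week 60 alone, although the planned Aim 6 analysis is change from baseline; the trigger should use the baseline value

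*Combined protocol and SAP*

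**What the plan says.** All references are to the combined protocol and SAP.

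- **Core Aim 6 cohort** (MATERIALS AND METHODS, Longitudinal study): "To address aim 6, all non-diabetic patients with TW 20 response followed until TW 60 will be included". Insulin is planned as "Fasting insulin levels at TW00 and TW 60 for patients with TW20 response". Neither is conditional on anything.
- **Trigger, same place, stated twice:** matched controls without a TW20 response "will also be studied if a difference in IR is detected at TW 60 between patients with SVR and relapsers"; and "If results show a difference in IR at TW60 between patients with SVR and relapsers, fasting insulin levels at TW20 will also be tested". No baseline term, covariate, test or alpha is given.
- **Analysis** (DATA ANALYSES, Longitudinal study, item 5): the correlation of HOMA-IR changes "from baseline to week 60 of the lead-in patients and virologic response or relapse". The paragraph that follows says "Changes in HOMA-IR would be calculated between the responder and relapser groups". It also plans a comparison of week 60 samples between the two groups. It then makes the week 20 work depend on differences being found, without saying whether in week 60 level or in change.
- **Link between insulin resistance and response:** Aim 4 is "To identify metabolic predictors of week 20 and sustained virologic response". BACKGROUND AND SIGNIFICANCE adds "We hypothesize that hepatic steatosis and increased insulin resistance independently predict nonresponse to PEG-IFN and ribavirin therapy for chronic HCV".
- **Baseline serum** (Specimen Collection, Handling, and Shipping, item 6): W00 serum goes to the insulin laboratory only for randomised patients.

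**The concern.** The decision rule and the analysis use different quantities. The rule looks at the level of insulin resistance at TW60; the analysis looks at change since baseline. Aim 6 asks whether clearing the virus improves insulin resistance, which is a within-patient change that a single later level cannot show.

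SVR and relapse are outcomes, not allocated arms, and Aim 4 treats metabolic factors as possible predictors of sustained response. The plan therefore cannot take baseline insulin resistance to be balanced between the two groups. Any baseline gap carried forward appears at TW60 as a difference, whatever clearance did. A gap in the other direction can hide a real improvement.

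At stake is the decision to run the TW20 assays and to assemble matched controls, plus the meaning of the raw week 60 comparison that DATA ANALYSES keeps beside the change analysis.

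**Working it through.** **The plan's own figure.** About 250 nondiabetic subjects with W60 sera, evenly divided: 250 / 2 = 125 per group, as stated. At about 80% nondiabetic this implies 250 / 0.80 ≈ 312 with W60 samples. The 250 itself cannot be derived from the documents, and no power, effect size or alpha is given.

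**Assumptions.** Two-sided alpha 0.05; log HOMA-IR in SD units; baseline gap d of 0 to 0.4 SD; baseline–W60 correlation ρ of 0.5 to 0.7; no clearance effect unless stated. None of these comes from the documents.

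**TW60-only trigger.** With a gap g still present at W60, the standard error is √(2/125) = 0.1265 and

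P(fires) = Φ(g/0.1265 − 1.96) + Φ(−g/0.1265 − 1.96).

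If the gap persists, g = d. If it regresses to the mean, g = ρd.

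| Baseline gap d | Gap persists | Gap regresses, ρ = 0.5 to 0.7 |
|---|---|---|
| 0 | 5% | 5% |
| 0.1 | 12% | 7–8% |
| 0.2 | 35% | 12–20% |
| 0.3 | 66% | 22–38% |
| 0.4 | 88% (up to 89% simulated) | 35–60% |

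Example: d = 0.3, persisting: 0.3/0.1265 = 2.372, and Φ(2.372 − 1.96) = Φ(0.412) = 66%. Example: d = 0.4, ρ = 0.7, regressing: g = 0.28, 0.28/0.1265 = 2.214, and Φ(0.254) = 60%.

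**Alternative triggers.** Simulation, 3000 runs per setting, no clearance effect, d = 0.2–0.4, ρ = 0.5–0.7:

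| Trigger | Gap persists | Gap regresses |
|---|---|---|
| Change score significant | 4–5% | 10–34% |
| ANCOVA on baseline significant | 11–43% | 4–6% |
| ANCOVA significant, change in same direction | 10–37% | not the problem case |
| Both significant | 2–3% | 2–3% |

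Neither single method is safe in both settings. Asking the change score only to agree in sign removes very little: at d = 0.3, ρ = 0.6, persisting, 22.0% becomes 21.6%.

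**Power with balanced baselines, true effect 0.3 SD.** TW60-only: about 66%. ANCOVA divides the standard error's scale by its gain, so the signal is 2.372/√(1 − ρ²): 2.739 at ρ = 0.5 and 3.321 at ρ = 0.7, giving 78% and 91% (simulated 76–91%). Both significant: 61–85%; a second run gave 64–86%, so read these to within a few points.

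**Masking.** If SVR patients start 0.3 SD higher, the gap persists and clearance lowers log HOMA-IR by 0.3 SD, the TW60 levels coincide. The TW60-only trigger then fires in 5%, against 75% for the change score at ρ = 0.6.

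**The case against.** The strongest reply is that this is a wording mismatch in an optional extension. Much of it stands.

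- **A reader might infer that Aim 6 itself hangs on the trigger.** It does not. The core cohort and its TW00 and TW60 insulin assays are unconditional; only the added controls and TW20 assays are gated.
- **A reader might infer that the plan expects SVR patients to start with lower insulin resistance than relapsers.** No section says so. The stated hypothesis concerns nonresponse, both groups here are TW20 responders, and the Aim 4 analysis of SVR pools week 20 nonresponders into the no-SVR group. The gap between SVR and relapse may be small or absent, and with no gap the trigger fires at 5%.
- **A reader might infer that the Aim 6 claim would rest on a pre-treatment difference.** The listed analysis is already change from baseline, which holds its level if a gap persists. If SVR patients start lower and the gap regresses, the change score errs against the claim that clearance helps.
- **The week 20 condition under DATA ANALYSES can be read as referring to change.** It can, but that section also plans a raw week 60 comparison, and the two earlier statements name TW60 explicitly.
- **Weight change should not be adjusted for.** Agreed for the main model: it is measured after baseline, and the plan argues that using W60 sera already limits the influence of on-treatment weight loss.

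What remains is that the rule as written omits a baseline value that the same section plans to measure.

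**Conclusion.** The point holds as a mismatch between the trigger and the planned analysis. That part is textual and needs no assumption. The size does: 125 per group is the plan's figure, while alpha, the baseline gap and the correlation are assumed. On those assumptions the false trigger rate runs from 5% with no gap to 89% with a persisting gap of 0.4 SD. Even with balanced baselines the rule gives up power that the baseline value would supply.

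The consequence is limited. A false trigger mainly spends assays and control samples, and a missed one forgoes the extension. The documents do not support the stronger reading that the Aim 6 conclusion is invalid. The change is worth making because it is cheap and specific.

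**What to change.** 1. Replace the TW60-only condition in both places in the Longitudinal study section, and the raw week 60 comparison under DATA ANALYSES, with one baseline-referenced contrast: log HOMA-IR, SVR against relapse, at a stated alpha. State that the week 20 condition under DATA ANALYSES means this contrast.
2. Report both the change from W00 to W60, as already planned, and ANCOVA of W60 log HOMA-IR on W00 log HOMA-IR. Trigger only if both are significant in the same direction.
3. Show results with and without weight change as sensitivity only.
4. Reconcile the shipping rule (W00 serum only for randomised patients) with the Aim 6 plan (TW00 insulin for TW20 responders). Patients still viremic at week 20 are the ones randomised, so, read literally, the rule leaves the Aim 6 cohort without baseline insulin. Every baseline-referenced analysis depends on this, including the one already listed.

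**Cost.** Items 1 to 3 are wording. Item 4 needs no assay beyond those the Aim 6 text already plans, but the W00 samples of TW20 responders must actually be sent. The joint rule loses some power against ANCOVA alone (61–85% against 76–91% for a true 0.3 SD effect with balanced baselines), which is the price of holding false triggers at about 2–3%.

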Patients will receive 6 months of combination therapy of interferon and ribavirin during the lead-in phase. Patients who remain viremic at treatment week 20 will be eligible for continued participation in this trial. These patients will be randomized to continue treatment with interferon alone for 3.5 years or no treatment. All patients will have repeat liver biopsies at the end of years 2 and 4.

This ancillary study will consist of a **cross-sectional** and a **longitudinal part**. In the following pages:

◆ Indicates additional data/sample collection for this ancillary study.

Schedule of Visits and Specimen Collection:

Cross-sectional Study – All tests performed at Screening (S00) or Baseline (W00).

This study will include all patients who remain eligible for continued participation in the NIH HALT-C trial after the lead-in phase. Baseline clinical data will be collected for all enrolled patients. Tests for insulin level and grading of liver biopsies for hepatic steatosis will not be performed until all patients have completed the lead-in phase to determine who will remain in the trial.

During the screening phase, clinical data will be collected and blood tests will be performed as part of the main protocol. Fasting blood glucose and triglyceride levels will be checked. Patients with known diabetes will be tested for glycosylated hemoglobin (HbA1c). These procedures are part of standard care of hepatitis C patients evaluated for interferon treatment and will be performed as part of the main protocol. An additional sample of blood will be collected for insulin level. Baseline liver biopsies will be scored for inflammation, fibrosis and iron. These assessments will be performed as part of the main protocol. The biopsies will additionally be graded for hepatic steatosis.

Baseline clinical data will be collected during the screenings or at baseline on:

- a) Sex, age, ethnicity, Form #1, Trial ID Assignment.
- b) Total body fat estimated by body mass index (BMI). BMI will be derived from body height and weight, Form #11, Physical Exam.
- c) ♦ Visceral fat estimated by waist circumference taken with a cloth tape at the level of the umbilicus, with the patient supine, Form #11, Physical Exam (See Appendix A for directions).
- d) Quantitative lifetime alcohol consumption and alcohol consumption during the year prior to entry into the Trial based on Skinner survey, Form #41.

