4. Aliquot serum into two tubes with 1 ml in each tube. Use standard 2 ml aliquot tubes supplied by the Repository These tubes should be labeled with the aliquot tube labels supplied by BBI and NERI. The specimens for this study will have a sequence number of 121 + 122. Collection of these specimens should be recorded on the appropriate Aliquot Form for this patient’s visit-Form #72-Lead in Phase Aliquot Form for W00 specimen and Form #73-Randomized Phase Aliquot form for M24 specimen.
5. Freeze at –80°C until shipment to the Central Repository. These specimens should be included in standard frozen specimen shipments to the Repository.
6. Frozen serum aliquots will be batch shipped to the University of Michigan Diabetes Research and Training Center from the Central Repository for insulin testing. Baseline (W00) frozen serum samples will be sent after all patients have completed the week 24 (W24) visit; only specimens from patients who have been randomized will be sent. Frozen serum specimens from month 24 (M24) will be shipped after all patients have completed the month 24 (M24) visit.

7. Shipments can be received weekdays. The repository will ship the samples to:

[name]
 [name]
 [name]
 [name]

Principal Investigator [name]: [contact] [contact]

8. [name] should be notified of these shipments. [contact]
 Email: [contact]

9. After each batch of insulin test results is obtained, the results will be recorded on Form #120, Fasting Insulin and data entered into the Trial Data Management System.

Assay procedures: A solid-Phase, chemiluminescent enzyme immunometric assay for the determination of serum insulin levels was developed for the IMMUOLITE automated immunoassay analyzer. In the 60-minute assay procedure, patient serum incubates with an immobilized monoclonal anti-insulin antibody and an enzyme-labeled polyclonal antibody.

- **Glycosylated Hemoglobin**

1. Local labs will be responsible for running glycosylated hemoglobin tests on patients with known diabetes.
2. Blood drawn for glycosylated hemoglobin can be collected in the same tube as for fasting glucose and triglycerides. These three tests can be run from 5 mls of whole blood.
3. Preparation of the blood for the tests should be done according to the local lab's guidelines.

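### Baseline and month-24 insulin samples of randomized patients are assayed in separate shipments with no linking samples, so a shift between runs cannot be told apart from mean change (minor)

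*Combined protocol and SAP*

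**What the plan says.** Step 6 of Specimen Collection, Handling, and Shipping sets two shipments to the insulin laboratory.

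- Baseline: "Baseline (W00) frozen serum samples will be sent after all patients have completed the week 24 (W24) visit". The same sentence adds a restriction: "only specimens from patients who have been randomized will be sent".
- Follow-up: "Frozen serum specimens from month 24 (M24) will be shipped after all patients have completed the month 24 (M24) visit".

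Step 9 has results recorded batch by batch ("After each batch of insulin test results is obtained"). The cross-sectional part of Schedule of Visits and Specimen Collection agrees on the timing of the first run: "Tests for insulin level and grading of liver biopsies for hepatic steatosis will not be performed until all patients have completed the lead-in phase".

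Step 4 banks two 1 ml serum tubes per visit: "The specimens for this study will have a sequence number of 121 + 122". The visit table at the front of the document assigns only sequence 121 to the insulin test. No use is stated for the second tube.

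The document does not mention linking samples, running a patient's two visits together, re-assay of stored baseline serum, or any adjustment for batch.

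In the list of longitudinal analyses, the only named change in an insulin measure is item 5: "Correlation between changes in insulin resistance (measured using the homeostasis model assessment (HOMA)) from baseline to week 60". M24 insulin is collected specifically for this ancillary study, but no listed analysis names it.

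**The concern.** For randomized patients, visit and shipment are the same variable: every W00 value comes from the first campaign and every M24 value from the second. Suppose the assay reads a few percent higher or lower in the second campaign. Every patient's insulin then moves in the same direction, and HOMA-IR, which is calculated from fasting insulin and glucose, moves with it. Nothing in the planned data would reveal this.

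The statement at risk is of the form: insulin resistance rose (or fell) between baseline and year 2, in the cohort or within one arm. A second use is also at risk. The cross-sectional risk factors include hyperinsulinemia as present or absent. If that coding is reused at M24 with a fixed cut-off, a shift moves patients across it and looks like new or resolved hyperinsulinemia.

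**Working it through.** The plan gives no sample size, assay precision or drift figure for insulin, so there is no figure of its own to reproduce.

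**1. Gap between the triggers.** The plan states: "Patients will receive 6 months of combination therapy of interferon and ribavirin during the lead-in phase". The randomized phase lasts 3.5 years. 6 + 42 = 48 months, which matches M48 as the end of year 4, so the month labels count from W00.

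- W24 in months: 24 × 7 / 30.4375 = 5.5.
- Gap: 24 − 5.5 = 18.5 months. It would be 24 months if M24 were counted from randomization at W24.

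**2. Can batch and time be separated?** Take a model for log insulin with a term for each patient, plus time, batch and time-by-arm. With six patients and two visits there are 9 columns.

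- As planned, the batch column equals the time column. The rank is 8 of 9, and it stays 8 when batch is removed.
- With two baseline aliquots re-assayed in the second run, the rank is 9 of 9.

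A few linking samples are thus enough to make the shift estimable.

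**3. What a common proportional shift s does.**

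- Log scale: each change becomes d + ln(1+s). The mean change is biased by ln(1+s). A difference between arms in mean change, or a correlation of changes, is untouched.
- Raw scale: the change becomes (1+s)y₁ − y₀ = d + s·y₁, where y₀ and y₁ are the true W00 and M24 values. The error depends on the patient's M24 level, so correlations of raw changes can be altered. A difference between groups is off by s times their difference in mean M24 level.

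**4. Size of a false mean change.** Assumptions, none from the document: s of 5% or 10%, SD of change in log insulin 0.5 to 0.7, no true change, two-sided 5% test. n = 450 is consistent with the remark in Data Analyses that the study will have 3 to 4 times the 148 patients of an earlier study (444 to 592).

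z = ln(1+s) / (SD/√n); probability of a significant result = Φ(z − 1.96) + Φ(−z − 1.96).

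| s | ln(1+s) | SD | SD/√450 | z | Falsely significant |
|---|---|---|---|---|---|
| 10% | 0.0953 | 0.5 | 0.0236 | 4.04 | 98% |
| 10% | 0.0953 | 0.7 | 0.0330 | 2.89 | 82% |
| 5% | 0.0488 | 0.5 | 0.0236 | 2.07 | 54% |
| 5% | 0.0488 | 0.7 | 0.0330 | 1.48 | 32% |

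A separate simulation used 400 patients and a within-visit SD of 0.3 on the log scale, again with no true change. Shifts of 0, 5, 10 and 15% gave a significant overall change in 5, 63, 99 and 100% of runs. The treated-versus-control difference in change was significant in about 4 to 6% throughout, as step 3 predicts.

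**5. Precision of a linking set.** With k re-assayed pairs and an assumed assay CV of 6 to 10%, the SE of the estimated shift is CV × √(2/k). For k = 60 and CV 6% this is 1.1%; for k = 40 and CV 10% it is 2.2%.

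**The case against.** The case for leaving step 6 alone has four parts.

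- **No listed analysis uses M24 insulin.** This stands. Longitudinal item 4 is open-ended but names BMI, alcohol, triglyceride, inflammation and iron. The false-positive rates above apply to a test of mean change that the plan does not list. Against this, M24 insulin is drawn expressly for this study, and comparison with baseline is its evident purpose.
- **Comparisons between arms and correlations are protected.** This stands for log-scale changes. The plan states no log transformation for insulin or HOMA-IR, so for raw changes the protection is only partial.
- **The drift is assumed.** This stands. One laboratory and one automated platform are used, and the document is silent on assay quality control. Silence does not show that control is absent.
- **The 18 months separate triggers, not assays.** This stands. Step 6 sets only the earliest date for each shipment. A late first shipment would shorten the gap, but the plan does not ask for a joint run.

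A reader might also infer that Aim 6 has the same fault, so that a finding of improved insulin resistance after viral clearance would be contaminated by drift. The document does not support that. Aim 6 concerns week-20 responders, whereas the early W00 shipment is limited to randomized patients, and randomization is described only for patients still viremic at week 20. No shipping rule exists for week-60 serum. Nothing prevents a responder's W00 and W60 samples from being run together; the rule is simply unwritten.

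**Conclusion.** The point holds for the W00-to-M24 comparison in randomized patients. As step 6 stands, a shift between runs is completely aliased with overall or within-arm mean change in insulin or HOMA-IR, and with any change in hyperinsulinemia status judged against a fixed cut-off. The aliasing follows from the text alone. Its size rests on assumed values for the shift and the SD: 82 to 98% false mean change at a 10% shift, and 32 to 54% at 5%, for about 450 patients.

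Severity is minor. The exposure is to descriptive or within-group change and to raw-scale analyses, on a measurement that no listed analysis names. Randomized comparisons of log-scale change are not threatened, and drift in the Aim 6 analysis is not established.

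**What to change.** Add to step 6 that about 40 to 60 banked second W00 aliquots (sequence 122) are re-assayed in the M24 run. Report the paired ratio of the two baseline readings with its confidence interval, and recalibrate the two runs to each other if the ratio differs from 1. The first baseline run can go ahead as planned.

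When a shipping rule is written for Aim 6, have each responder's W00 and W60 samples assayed in the same run, and include in that run W00 aliquots from patients measured in the first baseline run. The second part matters. If responders' baseline serum is assayed in a later run than nonresponders', batch lines up with response, and the Aim 4 comparison of baseline metabolic factors by response would be confounded in a way that does not cancel.

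The cost is a change of wording, a few dozen extra insulin assays and one reserve aliquot from each bridging patient. No new blood draw, visit or staff is needed.
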